Pediatric patients undergoing microdirect laryngoscopy and bronchoscopy (MDLB) pose anesthetic challenges of maintaining adequate oxygenation and ventilation while providing a motionless surgical field without an endotracheal tube. Given this challenge, we propose a prospective, randomized controlled trial to evaluate the use of high flow nasal cannula (HFNC) as transnasal humidified rapid-insufflation ventilatory exchange (THRIVE) in pediatric patients undergoing MDLBs.

Research Questions:

1. Can the use of HFNC during MDLB result in reduced oxygen desaturations as measured by the oxygen desaturation index (ODI) as compared to standard of care (SOC)?

2. Does the use of HFNC during MDLB result in a reduced number of oxygen desaturations below 90% during the procedure?

3. Does the use of HFNC during MDLB resulted in a reduced number of surgical interruptions?

AIM 1:

To prospectively determine if treatment with HFNC during MDLB reduces oxygen desaturations as measured by oxygen desaturation index (ODI) as compared to SOC in pediatric patients under general anesthesia. We hypothesize that participants receiving HFNC will demonstrate statistically improved ODI over participants receiving SOC. ODI is defined as a 4% decrease in saturation from a 120 second rolling mean for greater than 10 seconds.

AIM 2:

To determine if treatment with HFNC during MDLB results in a reduction in the number of desaturations below 90% and a reduction in the number of surgical interruptions as compared to standard of care in pediatric patients under general anesthesia. We hypothesize that participants receiving HFNC catheters will demonstrate statistically fewer desaturations over participants receiving SOC. Desaturations will be controlled by duration of procedure.

Abstract:

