Demographics and postoperative diagnoses in control and THRIVE were collected. Interruptions were defined as the need to pause surgery to provide airway support, such as mask ventilation or intermittent intubation. Pulse oximetry was recorded by second in the electronic medical record. ODI was defined as a 4% decrease in saturation from a 120 second rolling mean for greater than 10 seconds. TCO2 was recorded at procedure start and end. Adverse events (nausea, vomiting, sinus pain, throat pain, epistaxis) were recorded prior to discharge.

Outcomes were calculated using negative binomial regression with case duration as an offset in the unadjusted and adjusted models, with the exception of tCO2. Models were adjusted for postoperative diagnoses. 210 patients were screened and 67 (control = 36, THRIVE = 31) were included in the final analyses. There were no demographic group differences. P values are reported as (unadjusted value, adjusted value), respectively. There were no significant differences in surgical interruptions, tCO2, or adverse events. There were significant differences in ODI between groups (p=0.003, 0.005) and number of oxygen desaturations below 90% in the unadjusted model (p=0.039,0.082).

This was the first prospective study examining THRIVE's effectiveness during pediatric MDLBs. Although there were no significant differences in surgical interruptions, there were significant differences in ODI and oxygen desaturations when not adjusting for postsurgical diagnoses. Although THRIVE has been reported to potentially contribute to ventilation, these results do not support a difference. The table below summarizes these findings.

			β	p-value
Primary outcome	Number of Interruptions	Unadjusted	-0.70	0.13
		Adjusted for post- surgical diagnosis	-0.41	0.37
Secondary outcomes	ODI	Unadjusted	-1.78	0.003
		Adjusted for post- surgical diagnosis	-1.74	0.005
	Desaturations below 90%	Unadjusted	-1.25	0.039
		Adjusted for post- surgical diagnosis	-1.08	0.082
	Adverse Events	Unadjusted	-0.23	0.72
		Adjusted for post- surgical diagnosis	-0.33	0.64
	Final CO2*	Unadjusted	-1.93	0.55
		Adjusted for post- surgical diagnosis	-1.04	0.75

* = linear regression result, with case duration included as a covariate in both unadjusted and adjusted models

Summary

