Those enrolled in the intervention arm will be exposed to greater than minimal risk. Potential benefits to the intervention arm include improved oxygenation and ventilation, improved surgical operating conditions, prevention of oxygen desaturation, prevention of complications related to apnea or oxygen desaturations, prevention of atelectasis and any subsequent complications. Potential serious risk such as pneumothorax or pneumocephalus are exceedingly rare and will be minimized by careful observation of the patients during the duration of high-flow cannula application. Potential risks such as headache, sinus or nasal mucosal irritation, aspiration, and gastric insufflation are also low risk with less associated morbidity, but the researchers feel the potential benefits outweigh these risks. The potential risks and benefits will be provided to the parents or guardians when obtaining written consent prior to the procedure.

Methods:

This prospective, randomized, controlled trial is a multi-center collaborative project including the primary site - Lucile Packard Children's Hospital (Stanford University, Palo Alto, CA), Cincinnati Children's hospital (Cincinnati, OH), Lurie Children's Hospital (Chicago, IL), University of Virginia Children's Hospital

(Charlottesville, VA), Massachusetts Eye and Ear Infirmary (Harvard University, Boston, MA), and Boston Children's Hospital (Harvard University, Boston, MA).

The primary outcome measure will be oxygen desaturation index (ODI), as defined by a 4% decrease in saturation from a 120 second rolling mean for greater than 10 seconds. Secondary endpoints include the relative number of desaturations below 90% lasting greater than2 seconds as a function of overall case duration and the number of surgical interruptions, as defined by any time the procedure is temporarily halted due to suboptimal airway conditions.

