Preoperatively, medical history will be collected along with baseline physiological data (blood pressure, heart rate, age, weight, gender, medical conditions, medications and allergies). The Masimo pulse oximeter will be applied to the patient where appropriate prior to induction of anesthesia to obtain baseline oxygen saturation and heart rate and will remain on the patient until the patient has emerged from anesthesia. The THRIVE system will be placed on patients randomized to the treatment arm following induction of anesthesia and prior to initiation of the procedure. It will be removed following completion of the procedure and prior to emergence from anesthesia. Although this may pose a challenge in an active infant, the team will do its best to obtain baseline data prior to induction of anesthesia.

Physiological data (pulse oximeter and heart rate) will be collected real-time using the Masimo device. The heart rate and oxygen saturation will be continuously recorded by the Masimo device and data will be extracted to a research laptop via USB transfer following completion of case. The anesthesia monitors will record into EPIC anesthesia every 3 minutes according to anesthesia standard of care: (i) (non-invasively-measured) systolic/diastolic/mean arterial pressures; (ii) SaO₂; (iii) heart rate; (iv) end tidal CO₂; (v) end tidal volatile concentration and all drugs given; (vi) ventilator settings (vii) temperature. These vital signs will be recorded as is standard of care, but not collected by the study investigators, who will only gather the heart rate and oxygen saturation in two second intervals from the Masimo.

The following data will also be collected: (i) medical history; (ii) type and duration of anesthesia and surgery; (iii) any critical or adverse events.

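### Do two names for the scaling time, and an unstated counting window for the oxygen desaturation index, leave the desaturation analysis open?

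*Combined protocol and SAP*

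**What the plan says.** The below-90% endpoint is described in three places. Research question 2 asks about a "reduced number of oxygen desaturations below 90% during the procedure". Aim 2 adds: "Desaturations will be controlled by duration of procedure". The endpoint paragraph in Methods gives the number of such events "as a function of overall case duration".

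For the primary endpoint, Aim 1 and Methods both define an ODI event as a 4% fall from the 120-second rolling mean lasting more than 10 seconds. Neither says when counting starts or stops, or what the count is divided by. A per-time basis is implied in two places. The pilot in Preliminary Results used "negative binomial regression with case duration as an offset", and the sample size paragraph uses 0.119 events per minute over an average case of 30 minutes. The trial's own statistical analysis entry names no model or offset.

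Methods sets out the timing. The oximeter goes on before induction and stays on until emergence. For the cannula: "The THRIVE system will be placed on patients randomized to the treatment arm following induction of anesthesia and prior to initiation of the procedure". It comes off after the procedure and before emergence. The observer in the room records procedure start and end, and the study also collects "type and duration of anesthesia and surgery".

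**The concern.** The documents offer more than one clock: the procedure, the anesthetic and the full oximeter trace. The word *overall* in Methods can be read as the longest of these. Methods also says that the oximeter "data will be extracted to a research laptop via USB transfer following completion of case", and Preliminary Results speaks of case duration for the model but says "TCO2 was recorded at procedure start and end", so *case* and *procedure* might be different intervals.

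If they are, two analysts could produce two results. The full trace contains treatment-arm minutes without the cannula at both ends. Events in those minutes that the cannula cannot affect would dilute the rate ratio. The trial is unblinded, so a window chosen after the data are seen could be criticised. The pilot rate and the 30 minutes might also be on a different basis from the final analysis.

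**Working it through.** **1. The passages side by side.**

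| Question | Text | Points to |
|---|---|---|
| Which below-90% events count? | Research question 2; Potential benefits | Those within the procedure |
| What divides the below-90% count? | Aim 2 | Procedure duration |
| What divides the below-90% count? | Methods | Overall case duration |
| Which times does the observer record? | Methods | Procedure start and end |
| Does any text direct counting at induction or emergence? | None found | No |

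The two phrases therefore differ on the divisor alone. The evidence that *case* and *procedure* are distinct is thin. The remark about completion of the case only times a data transfer. In the pilot, carbon dioxide was read at procedure start and end, and the table footnote adjusts its final value for case duration, which fits use of the two words as synonyms at least as well.

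**2. What a different divisor does.** Inputs from the sample size paragraph: control rate 0.119 per minute, 30 minutes, 20% effect (read as a rate ratio of 0.80), theta 0.3609.

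- Control events per patient: 0.119 × 30 = 3.57. Treated: 3.57 × 0.80 = 2.856.
- Add 10 minutes to the divisor in both arms: 3.57/40 = 0.0893 and 2.856/40 = 0.0714; ratio 0.80.
- Add 30 minutes: 3.57/60 = 0.0595 and 2.856/60 = 0.0476; ratio 0.80.

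The reported rates fall and the treatment comparison does not move.

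**3. Whether duration matters for power.** The variance of the log rate ratio is (1/m_c + 1/m_t + 2/theta)/n, where m_c and m_t are mean events per patient and n is patients per arm. Power is Φ(|ln 0.80|/SE − 1.96), with two-sided 0.05 assumed because the plan states no alpha for this trial. I take 250 per arm, from 500 patients at 1:1.

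- 30 minutes: 1/3.57 + 1/2.856 + 2/0.3609 = 0.280 + 0.350 + 5.542 = 6.172; SE = √(6.172/250) = 0.157; power 29.5%.
- 15 minutes: power 27.2%. 60 minutes: power 30.8%.

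The plan's 82% is not reproduced at any of these durations, so the choice of clock does not explain that gap, which is a separate matter. Between-patient dispersion supplies 5.542 of the 6.172, so the length of the window has little influence.

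**4. What dilution would require.** Suppose a share s of control events in the full trace fell outside cannula time and was unaffected by treatment. The ratio would then read 0.80 + 0.20s, for example 0.82 at s = 0.10. This needs events to be counted over the whole trace, a step beyond the quoted difference that no text directs. It also needs a value for s, which the documents do not give. No size can be attached to it.

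**The case for a change.** The strongest reply is that the primary endpoint should not depend on inference. Most uses of the phrase about the airway examination (Aim 1 and the research questions) attach grammatically to the use of the cannula, not to the counting of events; only research question 2 and the benefits text place desaturations themselves inside the procedure, and both concern the below-90% endpoint. The pilot's offset belongs to a finished study and does not say which events were counted. With an open-label design, explicit wording would remove an argument later.

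Part of this stands: the ODI window and divisor are implied, not written. But the competing reading has no positive support, and one sensible default is available from data already collected.

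The contrast between the windows is also one of degree. The consent section provides for removing the cannula if it interferes with surgery or anesthesia, and the risk section allows it to be paused for an adverse event, so cannula-off minutes can fall inside the procedure too.

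The equal-lengthening condition in step 2 is also an assumption. If the two clocks differed by unequal proportions between arms, the ratio would shift; the documents give no figures to judge by how much. The procedure window has weaknesses of its own: it is timed by an unblinded observer and can be lengthened by interruptions, which are a secondary outcome. Finer rules, such as scope-based markers, event-onset conventions or a whole-trace sensitivity analysis, are therefore design preferences and not corrections of an error.

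**Conclusion.** No change to the plan follows. The two duration terms are undefined and probably synonymous, and the missing ODI window is a detail that an analyst would fill by counting from recorded procedure start to recorded procedure end, with the log of that duration as offset. On the plan's inputs, changing the divisor alone leaves the rate ratio at 0.80 when the added time is equal in both arms, and power moves only from 27.2% to 30.8% across 15 to 60 minutes. Dilution toward 1 would arise only if events were counted over the whole trace, which the plan does not ask for, and its size cannot be estimated from the documents. The conclusion assumes that the analyst follows the procedure-based reading and that the pilot's 0.119 per minute and 30 minutes are on a comparable basis, which the documents do not confirm.

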Randomization method: The method of randomization is simple randomization. Prior to study initiation, the study statistician will provide the randomization schedule through REDCap. At study conclusion, descriptive analyses will be conducted prior to hypothesis testing to evaluate the success of the randomization procedure in equally distributing patient characteristics (such as age, gender, past medical history, type of procedure, type of supplemental oxygen, etc.).

Retention of patients: Retention of patients is a consideration in every study and random attrition may reduce statistical power. Systematic attrition threatens the external validity of the results (such as if a subgroup of participants tend to discontinue the study, generalizability may be compromised). Differential attrition may reduce validity when comparing conditions if baseline variables correlate with outcome. Retention will be analyzed with chi-square and life table methodology and is anticipated to be low. We will examine closely the enrollment of targeted patients at month 6 and 12. If, at these time points, we discover that the recruitment is below anticipated volume, we will immediately contact our colleagues at other sites. CHOP is the most likely additional sites given preliminary interests that have been expressed from anesthesiologists there.

Payment:

There is NO financial benefit or reimbursement for participation in the study.

References:

